## **Resveratrol in Human Subjects**

### **RATIONALE**

Since a causal link between Sirt1 and aging and diabetes related metabolic changes has not yet been established in humans, this protocol is indispensable to establishing the clinical relevance of this program. Sirt1 shows significant potential as a useful therapeutic target that can be used in ameliorating many of the conditions associated with the metabolic decline of aging and in Type 2 diabetes. We are particularly interested in investigating the role of Sirt1 in the regulation of glucose homeostasis, insulin action and mitochondria function in humans. Furthermore, demonstrating the ability of resveratrol to reverse the metabolic changes of aging and Type 2 diabetes would be of tremendous therapeutic importance, particularly in light of the feasibility and safety of longterm administration of this orally available agent.

Our decision to study middle aged subjects is primarily due to the importance of timing this intervention to decrease aging-related metabolic changes prior to the presentation of serious age-related diseases. An additional advantage is the feasibility of recruiting and studying subjects of this age group with somewhat arduous insulin clamp studies, biopsies and muscle function tests, as compared to a frailer group of elderly subjects. Our preliminary studies, shown below, indicate that individuals above 40 years of age already have substantial age-related declines in insulin sensitivity that would be appropriate targets of intervention. Additionally, since resveratrol appears to exert more beneficial effects in animal models of caloric excess, overweight subjects will be recruited for these studies. Similarly, subjects with Type 2 diabetes have established insulin resistance and nutrient excess as demonstrated by elevated free fatty acids and are likely to benefit from this intervention.

The proposed *in vivo* studies will permit the study of effects on insulin action in concert with effects on adipose macrophage content and activation and muscle function, as well as circulating inflammatory mediators. Such a comprehensive analysis would be necessary to adequately connect the entire hypothesis in humans.

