### **Aim 1: To study the effects of resveratrol on age-related insulin resistance**

*We hypothesize that treatment of overweight, middle aged or Type 2 diabetes subjects with resveratrol will result in improved insulin sensitivity, as demonstrated by increased insulin-stimulated glucose uptake and enhanced insulin-mediated suppression of glucose production.*

We will study the following subject group:

- **Overweight and either young or middle aged** (BMI 25-30 kg/m^2, age 21-65) nondiabetic subjects, n=40 diabetic subjects (BMI=25-35) n=15

Each subject will receive a 28 day course of **resveratrol** (n=55). RevGenetics will supply the resveratrol (500 mg capsules; 2 capsules bid) for our proposed studies. A certificate of analysis has been provided by the manufacturer.

A comprehensive study of whole-body insulin action will be undertaken with specially designed „stepped” euglycemic (~90 mg/dl) -hyperinsulinemic clamp studies, both before and after administration of resveratrol.

Thus, we will compare the following parameters under paired conditions in each subject, on day 0 and day 28 of resveratrol treatment:

- a. **hepatic insulin action:** this will be determined as the ability of low infusion rates of insulin (20 mU/m^2.min above basal requirements) to suppress glucose production during the “**low insulin phase**” of the clamp studies.
- b. **peripheral insulin action:** this will be determined as the ability of high infusion rates of insulin (80 mU/m^2.min above basal requirements) to stimulate glucose uptake during the “**high insulin phase**” of the clamp studies.

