***These techniques are approved by the CCI under Protocols 2000-200 and 2006-414.***

**Aim 2: To examine the effects of resveratrol on systemic inflammation and/or on adipose tissue macrophages.**

This aim will make use of the **adipose biopsy specimens from Aim 1**. We will therefore examine the effects of resveratrol on macrophage content and activation in adipose tissue, and on systemic markers of inflammation, in **the same n=55 overweight, middle aged** (age 45-65) nondiabetic and diabetic subjects. We will be utilizing the younger 21-44 year old population to assess whether resveratrol has the same beneficial effects in younger subjects.

*We hypothesize that treatment of insulin resistant subjects with resveratrol will lead to reductions in systemic inflammatory markers and reduced content and/or activation of adipose tissue macrophages.* Systemic inflammatory markers to be measured will include TNF-a, IL-6, IL-1b, MCP-1. Adipose tissue macrophages will be isolated from subcutaneous abdominal adipose tissue, and will be quantified by fluorescence activated cell sorting (FACS) analysis. Gene expression of a variety of pro-inflammatory and pro-atherosclerotic factors will be examined by „real-time“ rt-PCR, to determine how resveratrol affects activation of adipose macrophages.

Following administration of resveratrol (n=55) for 28 days, we will examine:

1. Adipose macrophage content, by fluorescence activated cell sorting (FACS) analysis. These data will additionally be confirmed by immunohistochemistry
2. Activation of adipose macrophages, as assessed by expression and production of a variety of pro-inflammatory and pro-atherosclerotic factors, using „real-time“ rt-PCR and immunohistochemistry
3. Plasma levels of cytokines and acute phase reactants

**Adipose biopsy specimens-** Adipose biopsy specimens will be obtained as described above. Suctioned adipose tissue samples will be suspended in PBS and washed with a 40 µm cell strainer. Approximately 1 gram of tissue will be immediately homogenized in Trizol (Life Technologies, Bethesda, MD) with a Tissumizer homogenizer. This technique will ensure optimized yields of mRNA by the inhibition of RNases. The homogenate will be frozen on dry ice, transported to the laboratory and stored at -80°C. Subsequent mRNA extraction and analysis of gene expression will be performed in the Gene Expression Core lab. Remaining fresh adipose biopsy specimens will be immediately processed as described below.

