### STATISTICAL ANALYSIS

Data collected from each subject will be edited, entered, verified and entered into a FoxPro data base system in the GCRC. Data quality checking will be performed by computer programs designed to detect errors using accepted ranges, logic checks, and missing values. Outliers will be checked against the original record and correct values will be entered into a final data file. Data from FoxPro files will be transferred into SAS System Version 6.12 (SAS Institute, Cary, NC) for analysis. We shall utilize SAS for all data management and statistical analysis. Descriptive statistics of all the variables at different time points will be derived and reported.

For the specific aims of this study, repeated measurements of several parameters including glucose metabolism and gene expression will be measured in each subject, with the principal endpoint being the rate of whole-body glucose uptake during the final hour of the high insulin clamp. The null hypothesis is that glucose uptake will be equal in each pair of experiments (ie. prior to and following 45 days" treatment with resveratrol or placebo). To determine the changes in glucose uptake between the paired experimental protocols for each subject group, paired Student's t-tests will be performed. For *between-group* comparisons (ie. between the two subject groups randomized to resveratrol or placebo), the principal endpoint will be the difference in whole-body glucose uptake ( $\Delta$ GU) between the 2 experimental conditions (eg. Resveratrol vs. placebo), with null hypothesis that the response to the experimental intervention will be the same in all subject groups. To determine the changes in glucose uptake between the paired experimental protocols for each subject group, analysis of

variance (ANOVA) will be performed by using PROC GLM in the SAS statistical package. Within group effects will be derived from the analysis.

*All values will be presented as the mean +/- SE.*

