##### **Human Subject Characteristics**

The study population will consist of at least 40 nondiabetic subjects and 15 diabetic subjects with the following characteristics: ages 21-65 years, with BMI between 25 and 30 kg/m^2. The following subjects will be specifically excluded: children, mentally disabled persons, prisoners, pregnant women, fetuses, subjects with a history of ethanol or drug or toxin exposure which could be associated with neuropathy, any subject deemed incapable of giving voluntary informed consent, and subjects with a history of a bleeding disorder or with a prolonged PT or PTT; a history of uterine, breast, or ovarian cancer, renal disease, and liver disease or impairment. Women in the child-bearing age-group will be allowed to participate, provided they have negative pregnancy tests. The research topic to be studied is not relevant to the involvement of special classes or groups of subjects and therefore no criteria for their involvement are specified.

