**2. ADEQUACY OF PROTECTION AGAINST RISKS****Recruitment and Informed Consent Procedures:**

We will recruit at least 40 overweight, middle aged, nondiabetic subjects and 45 subjects with Type 2 diabetes by local advertising. Consent will be initially obtained during telephone screening performed by a research fellow or the study coordinator. Formal consent procedures which adhere to the Committee on Clinical Investigations of the Albert Einstein College of Medicine will be followed. Specifically, each subject will be verbally informed in layman's language of the purpose, benefits and possible risks of the studies. They will then read the written consent form in the presence of a member of the research team and a physician who will answer any further questions. The subject and

witness shall be asked to sign the consent form which will be kept in the patient's chart. Each subject's potential participation in related experiments (for example, when each subject is asked to perform repeat studies) will be explicitly stated.

All clinical data on the subjects will be confidential. Data generated in these studies will be considered only relevant for research purposes and will not be included in any clinical databases or the patient's chart. Since the GCRC databases are coded, the study data will not be available on any clinical database system.

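### The tests planned cannot show whether younger subjects get the same effect from resveratrol, and the between-group ANOVA is worded for a placebo comparison the trial does not have

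*Combined protocol and SAP*

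**What the plan says.** The age question is put in the sections for Aims 2, 3 and 4: subjects aged 21-44 are to be used "to assess whether resveratrol has the same beneficial effects in younger subjects". The 45-65 group set against them is described as both nondiabetic and diabetic. No size is given for the younger group.

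The diabetes groups come from the Aim 1 section, "nondiabetic subjects, n=40 diabetic subjects (BMI=25-35) n=15", and from Human Subject Characteristics, "at least 40 nondiabetic subjects and 15 diabetic subjects". The recruitment and consent section instead says "45 subjects with Type 2 diabetes by local advertising".

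Statistical Analysis plans paired t-tests on glucose uptake for each subject group. For between-group comparisons it sets a "null hypothesis that the response to the experimental intervention will be the same in all subject groups", and it says that analysis of "variance (ANOVA) will be performed by using PROC GLM in the SAS statistical package". The same section explains between-group as "between the two subject groups randomized to resveratrol or placebo". Yet General Experimental Conditions describes an open-label study, and in Aim 1 every subject receives resveratrol.

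The plan gives no significance level, SD, margin, variance assumption, covariate, CI for a difference between groups, or rule for reading a non-significant result. Values are to be shown as mean and SE.

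**The concern.** Asking whether an effect is the same in two groups is a question about the size of a difference. A test whose null is no difference can reject sameness but cannot establish it. Separate within-group tests do worse, because they invite a comparison of two p-values when the quantity of interest is one difference.

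A second problem arises if the ANOVA is carried over to the groups that exist. An ordinary ANOVA pools the variance. With unequal group sizes, such as 40 and 15, that is safe only if the two SDs of change are similar. The groups differ physiologically, and the plan gives no SDs.

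At stake is the answer to a stated question of Aims 2-4, and the reliability of any diabetic v nondiabetic comparison. The before-after test of glucose uptake within a group is not affected.

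**Working it through.** **Inputs.** From the documents: 40 nondiabetic and 15 diabetic subjects, 55 in all; age groups 21-44 and 45-65; between-group method PROC GLM ANOVA. Assumed, because the documents do not say: two-sided 5% level; normally distributed changes; age splits of 20 v 20 and 30 v 25; ratio r of the diabetic to the nondiabetic SD of change between 0.5 and 2. The illustrative gain of 0.454 SD is the one that 40 subjects detect with 80% power in a paired test. The plan has no power figure to reproduce; 40 + 15 = 55 is its only sample size arithmetic.

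**1. Significant in one group only, when both groups gain 0.454 SD.** With paired-test powers p and q (noncentral t), the chance that exactly one group is significant is p(1−q) + q(1−p).

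| Split | p | q | Exactly one significant |
|---|---|---|---|
| 20 v 20 | 0.487 | 0.487 | 2 × 0.487 × 0.513 = 0.50 |
| 30 v 25 | 0.671 | 0.587 | 0.671 × 0.413 + 0.587 × 0.329 = 0.47 |
| 40 v 15 | 0.800 | 0.374 | 0.800 × 0.626 + 0.374 × 0.200 = 0.58 |

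Identical effects therefore give discordant p-values about half the time.

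**2. A non-significant difference.** If one group gains 0.454 SD and the other nothing, the two-sample test (equal SDs) misses the difference 71% of the time at 20 v 20, 62% at 30 v 25 and 69% at 40 v 15.

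The 95% CI half-width for the difference, in SD units of change, is t × √(1/n₁ + 1/n₂):

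- 20 v 20: 2.024 × 0.316 = 0.64
- 30 v 25: 2.006 × 0.271 = 0.54
- 40 v 15: 2.006 × 0.303 = 0.61

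Even with a true difference of zero, equivalence at 40 v 15 (two one-sided 5% tests) would be shown about 5% of the time at a margin of 0.5 SD, 67% at 0.8 SD and 90% at 1.0 SD.

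**3. Pooled ANOVA at 40 v 15.** Set the nondiabetic SD to 1. The pooled variance is on average (39 + 14r²)/53, so the ANOVA takes the variance of the difference to be that figure times (1/40 + 1/15) = 0.0917. The true variance is 1/40 + r²/15.

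- r = 2: the ANOVA uses (95/53) × 0.0917 = 0.164; the truth is 0.292. The standard error is too small by a factor √(0.292/0.164) = 1.33.
- r = 0.5: the ANOVA uses (42.5/53) × 0.0917 = 0.074; the truth is 0.042. The standard error is too large.

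Integrating over the sampling distribution of both variances gives the actual type I error:

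| r | Pooled ANOVA | Welch |
|---|---|---|
| 0.5 | 1.1% | 5.0% |
| 1 | 5.0% | 5.0% |
| 1.5 | 10.1% | 5.1% |
| 2 | 14.1% | 5.1% |

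Simulation with 40,000 runs agrees (1.1%, 10.4% and 14.0% at r = 0.5, 1.5 and 2).

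**4. Does this carry over to age?** For near-balanced splits and r from 0.5 to 2, the pooled test stays close to nominal: about 4.9-5.5% at 27 v 28 and 3.9-6.6% at 30 v 25. At 40 v 45, the sizes implied by the recruitment section, it is about 4-6%.

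**5. The cut at 45.** For ages uniform over 21-65 and a linear trend (both assumed), a two-group split keeps 3p(1−p) of the information in age. With p = 24/45 this is 3 × 0.533 × 0.467 = 0.75. The cut costs precision rather than type I error.

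**The case against.** The strongest objection is that the plan never specifies an ANOVA of diabetic v nondiabetic, or of younger v older. Its between-group wording is tied to resveratrol and placebo. That is right, so the calculation at 40 v 15 shows what follows if the section is applied to the actual groups. The inference is fair, because no other groups exist and no other analysis text covers them, but it remains an inference.

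Several stronger readings are tempting, and the documents do not support them:

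- *The error rate is far from 5%.* No SDs are given; with equal SDs the ANOVA is exact.
- *The error problem also affects the age comparison.* Age-group sizes are not stated, and near-balanced groups stay near 5%.
- *The plan asks whether diabetic subjects respond the same.* Aims 2-4 ask this only for the younger subjects.
- *The plan will read non-significance as sameness.* No text says so. The aim wording and the lack of a margin leave room for it, no more.
- *The cut at 45 contradicts the Rationale.* The statement that "individuals above 40 years of age already have substantial age-related declines in insulin sensitivity" justifies studying people over 40; it does not rule out a boundary at 45.
- *Age and diabetes will not be modelled together.* The plan names no model terms, and PROC GLM could hold both.

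It can also be said that a pilot study need not carry a formal equivalence test. That stands, and it is a reason to ask for estimates with CIs instead.

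**Conclusion.** The concern holds in this limited form. The Aims 2-4 question about younger subjects cannot be answered by the tests in Statistical Analysis, and the between-group text describes a comparison the trial does not contain. This part does not depend on unequal SDs: discordant p-values arise about 47-58% of the time under identical effects, and the difference is known only to within 0.54-0.64 SD. Those figures rest on the assumed gain of 0.454 SD, the assumed splits, normality and a two-sided 5% level.

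The type I error of about 1% to 14% is conditional. It applies only if the ANOVA is used on 40 v 15 and the SD ratio lies between 0.5 and 2. It falls away if the SDs are equal, and largely if 45 diabetic subjects are enrolled.

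**What to change.** In Statistical Analysis:

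1. Replace the resveratrol v placebo wording with the groups that exist, and reconcile the number of diabetic subjects (15 or 45). Also reconcile the middle-aged n (55 in Aim 2; 25 in Aims 3 and 4), and state the expected age-group sizes.
2. For glucose uptake and for key endpoints of Aims 2-4 named in advance, model each subject's change on age in years and diabetes status together, with separate variances by diabetes status (Welch/Satterthwaite).
3. Report the age slope per decade and the diabetic-minus-nondiabetic difference with 95% CIs, and say what differences the intervals exclude.
4. State that p>0.05, or significance in one group only, does not establish sameness.
5. Keep the split at 45 for description only.

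The cost is some SAP wording and a procedure that allows separate variances; no extra subjects, visits or assays are needed. The slope assumes a roughly linear age trend, and if diabetic subjects are mostly older, the two contrasts will be less precise. The main downside is that a claim of the same effect becomes harder to make.

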## HUMAN SUBJECTS RESEARCH SECTION

### **Protection of Human Subjects**

#### **1. RISKS TO THE SUBJECTS**

##### **Human Subjects Involvement**

Subject involvement will include a preliminary screening visit for history, physical exam and lab testing to determine eligibility. Subsequently, each subject will participate in two infusion studies with frequent blood glucose monitoring.

##### **Human Subject Characteristics**

The study population will consist of at least 40 nondiabetic subjects and 15 diabetic subjects with the following characteristics: ages 21-65 years, with BMI between 25 and 30 kg/m^2. The following subjects will be specifically excluded: children, mentally disabled persons, prisoners, pregnant women, fetuses, subjects with a history of ethanol or drug or toxin exposure which could be associated with neuropathy, any subject deemed incapable of giving voluntary informed consent, and subjects with a history of a bleeding disorder or with a prolonged PT or PTT; a history of uterine, breast, or ovarian cancer, renal disease, and liver disease or impairment. Women in the child-bearing age-group will be allowed to participate, provided they have negative pregnancy tests. The research topic to be studied is not relevant to the involvement of special classes or groups of subjects and therefore no criteria for their involvement are specified.

**Table I DEMOGRAPHY OF RECRUITMENT AREA**

\*Data from United States Census 2000 (<http://www.census.gov/>)

	Bronx	Manhattan	Westchester County (Borders the Bronx)
Population	1, 332,650	1,537,195	923,459
Racial Distribution			
White (Non-Hispanic)	15%	50%	65%
Hispanic	48%	24%	16%
African American	36%	14%	14%
Asian	3%	10%	5%
Age Distribution			
>25 years	40%	27%	32%
25-44 years	31%	38%	31%
45-64 years	19%	23%	23%
65+ years	10%	12%	14%

**Table II TARGETED/PLANNED ENROLLMENT: Number of Subjects**

ETHNIC CATEGORIES	Sex/Gender		
	Females	Males	Total
Hispanic or Latino	8	8	16
Not Hispanic or Latino	12	12	24
Ethnic Category: Total of All Subjects	20	20	40
RACIAL CATEGORIES			
American Indian/Alaska Native	0	0	0
Asian	0	0	0
Native Hawaiian or Other Pacific Islander	0	0	0
Black or African American	8	8	16
White	12	12	24
Racial Categories: Total of All Subjects	20	20	40

**Sources of Materials/Use of Data:**

All data and records obtained in this study will be used for research purposes only. The protocol will be submitted for review and approval by the Institutional Review Board known as the Committee on Clinical Investigations of the Albert Einstein College of Medicine of Yeshiva University (CCI). The CCI is responsible to ensure human subject protections in compliance with institutional policies and federal regulations including the HIPAA privacy law.

**Potential Risks:**

Potential risks to the subjects include the following:

1. Blood withdrawal: The total amount of blood sampled will not exceed 190 ml per study, less than half of that donated by a blood donor.
2. 20% dextrose: The infusion of 20% dextrose may be associated with local venous irritation. This will be minimized by use of a large-bore antecubital vein in which the glucose will be infused.
3. D2G: is a non-radioactive glucose tracer and is not associated with any known side effects at the doses used.
4. Glucagon infusion in high doses can cause gastrointestinal symptoms such as cramps and nausea, and produce hyperglycemia in persons with glucose intolerance. The doses to be employed here are intended to maintain plasma glucagon at basal levels.
5. Growth Hormone: At higher doses and for prolonged periods of exposure, growth hormone (rhGH) has either insulin-like or insulin-antagonistic effects on carbohydrate and lipid metabolism, however the proposed infusion is for physiological replacement during SRIF infusion and is unlikely to have adverse effects.
6. Hypoglycemia: is unlikely to develop in these subjects because of the desired plasma glucose targets (90 mg/dl during the normoglycemic studies), the low rates of insulin infusion, and the constant blood glucose monitoring.
7. Resveratrol: Resveratrol is present in significant amounts in a variety of foods, including grapes, blueberries, peanuts and red wine and over-the-counter resveratrol supplements are widely used. Formal safety testing is not required for marketing of nutritional supplements, but to date, there have been no published reports of side effects at the commonly used doses (up to 1000 mg /day). A number of *in vitro* studies have demonstrated that resveratrol can be an inhibitor of various cytochrome P450 enzymes that are involved in drug metabolism. The relevance of these *in vitro* observations to *in vivo* use is unclear primarily because oral resveratrol is rapidly metabolized by the liver, free resveratrol levels are quite low and resveratrol metabolites have not been shown to be inducers or inhibitors of CYP enzyme activity. Nonetheless, caution is warranted, especially for drugs with a narrow therapeutic window (anti-epileptics, mexilitene, quinidine, cyclosporine, tacrolimus, HIV protease inhibitors) and use of these drugs will be exclusionary for this study. Furthermore, due to the potential estrogenic effects of resveratrol, a medical history of ovarian, uterine, and breast cancer will be exclusionary for the study.
8. Somatostatin: At the proposed physiological replacement doses has no known side effects.
9. Ocreotide: At the proposed physiological replacement doses has no known side effects.

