### **EXPERIMENTAL APPROACH AND METHODS:**

#### **STUDY POPULATION AND RECRUITMENT**

Overweight, middle aged and type 2 diabetes subjects will be recruited by a variety of approaches, as described below. Subjects will range in age from 21 to 65 years, will be overweight (BMI 25-30 kg/m^2) with and without diabetes mellitus. All subjects with a history of liver disease or liver abnormalities, hyperlipidemia, hypertension, heart disease, cerebrovascular disease, seizures, bleeding disorders, muscle disease, a known history of ovarian, uterine, breast cancer or smoking will be excluded. The following subjects will also be specifically excluded: mentally disabled persons, prisoners, pregnant women, subjects with a history of ethanol or drug or toxin exposure which could be associated with neuropathy, any subject deemed incapable of giving voluntary informed consent, and subjects with a history of a bleeding disorder or with a prolonged PT or PTT. Furthermore, subjects allergic to Novocain, Benzocaine and Lidocaine will also be excluded. Given potential concerns (based on *in vitro* observations) that resveratrol might inhibit various cytochrome P450 enzymes involved in drug metabolism, use of the following drugs will be exclusionary for this study: anti-coagulant and anti-platelet drugs, anti-epileptics, mexilitene, quinidine, cyclosporine, tacrolimus, and HIV protease inhibitors (see below under Protection of Human Subjects). NSAIDS should be avoided as far as possible during the study period. Additionally, given confounding effects of extreme exercise on muscle triglyceride content, highly trained or professional athletes will be excluded from the studies.

Women in the child-bearing age-group will be allowed to participate in the studies provided that they have negative pregnancy tests within a week of the studies and that they are not breast-feeding. Children below the age of 18 will be excluded from the current protocol, given the use of labeled isotopes. Prior to their enrollment in the study the purpose, nature, risks and benefits of the study will be explained to all subjects and their voluntary, informed, written consent will be obtained. All subjects will have a screening visit to allow for clinical evaluation, including history, physical examination and consent procedures.

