### **Recruitment and Screening Strategies for Clamp Studies**

Recruitment of middle aged subjects will be predominantly by local advertising. This will include posting flyers within Einstein and around the neighborhood and posting advertisements in area newspapers. [name]" research group has had considerable success with these approaches in the recruitment of many middle aged, nondiabetic subjects to date.

**Screening:** This visit will include a full history and physical examination, an oral glucose tolerance test and additional laboratory tests to determine eligibility, including serum electrolytes, BUN and creatinine, PT/PTT, liver function tests, CPK, and lipid profile, as well as a screening urinalysis, urine toxicology screening, and blood pressure measurements. Safety laboratories will be repeated during the first and second pancreatic clamp studies and include: CBC, chemistry, liver function tests, CPK, and urinalysis.

All subjects will present to the CRC fasting; consequently, visits will be scheduled in the morning. The oral glucose tolerance tests (only non-diabetic subjects) will consist of a 75g oral glucose challenge in the form of a beverage, with fasting (immediately prior to drinking beverage) and 2 hour venous blood samples for plasma glucose and insulin measurements. Physical examination will include a careful assessment of upper extremity veins, as well as measurement of height and waist circumference and percent body fat (by body impedance absorptiometry). Since public transportation in our local area is limited and many area residents do not drive, we will make arrangements to provide transportation to and from clinic visits, including screening visits, for all participants who require it.

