### **General Experimental Conditions:**

On the day of the first pancreatic clamp study the patients will receive a 28 days" supply of resveratrol capsules. The pilot study will be an open-labeled study. The study design requires that all 55 subjects participate in all of the proposed studies, as outlined below. Consequently, additional subjects will be recruited to compensate for those subjects who cannot complete all of the required studies.

Prior to each study, subjects will meet with study personnel to discuss dietary recommendations. Each subject will be instructed to follow a standardized diet plan for three days prior to each of the clamp studies (40% fat: 20% saturated, 10% polyunsaturated, 10% monounsaturated; 35% carbohydrate; 25% protein). Subjects will be asked to refrain from vigorous exercise for three days prior to each clamp study.

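### Resveratrol supplement users are not excluded and outside use is neither barred nor recorded, so the day-0 clamp is not assured to be an untreated baseline and the paired change could be biased toward no effect

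*Combined protocol and SAP*

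**What the plan says.** All references are to the combined protocol and SAP.

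- **Availability.** Potential Risks, item 7, states that "over-the-counter resveratrol supplements are widely used" and reports no published side effects "at the commonly used doses (up to 1000 mg /day").
- **Study dose as written.** Aim 1 gives "500 mg capsules; 2 capsules bid".
- **Comparison.** Aim 1 compares each subject "on day 0 and day 28 of resveratrol treatment". General Experimental Conditions describes the pilot as open-label, and all 55 subjects receive resveratrol. The schedule places dosing on days 1-28, after the first clamp and biopsies.
- **Drug exclusions.** Study Population and Recruitment says "use of the following drugs will be exclusionary for this study: anti-coagulant and anti-platelet drugs", then adds anti-epileptics and a few other named drugs. Human Subject Characteristics, Potential Risks and Protection Against Risk give overlapping lists. None names resveratrol or any supplement.
- **On-study drug restriction.** "NSAIDS should be avoided as far as possible during the study period". Nothing comparable is said about supplements.
- **Screening.** "This visit will include a full history and physical examination, an oral glucose tolerance test and additional laboratory tests to determine eligibility". No supplement question or resveratrol level is listed.
- **Diet.** "Each subject will be instructed to follow a standardized diet plan for three days prior to each of the clamp studies". The plan fixes fat, carbohydrate and protein shares only.

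**The concern.** In a before-and-after design with no concurrent control, the estimate is only as good as the baseline. Here day 0 has to stand for no resveratrol. The protocol itself says the compound is in common use, and the rules as written would not turn away someone who takes it daily.

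If resveratrol works, such a subject's day-0 measurements may already contain part of the effect, and the day-28 minus day-0 change would understate it. Aims 2 to 4 use the same subjects and the same two time points as Aim 1, so one contaminated baseline reaches every aim. The direction is toward no change, and a null result could not be told apart from prior exposure. Because outside use is not recorded, no later sensitivity analysis could separate users from non-users.

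The protocol does control other influences on these endpoints: it excludes highly trained athletes and asks subjects to avoid vigorous exercise for three days before each clamp. Silence on the study compound looks like an oversight rather than a policy of minimal restriction.

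**Working it through.** **Is there a figure to reproduce?** No. The Statistical Analysis section specifies paired t-tests but gives no alpha, power, effect size or standard deviation. The sizes below are conditional illustrations.

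**Step 1: is the restriction anywhere?** Study Population and Recruitment, Recruitment and Screening Strategies, General Experimental Conditions, the schedule, Human Subject Characteristics, Potential Risks and Protection Against Risk are the places where such a rule would sit. None contains an exclusion of users, an off-supplement interval, an on-study bar or a record of use.

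**Step 2: dilution of the paired mean.** Let f be the fraction of subjects using resveratrol at day 0 and g the share of the treatment effect already present in them. If users end at the same day-28 level as non-users:

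expected mean change = (1 − f × g) × true change, so the proportional loss is f × g.

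Neither f nor g is in the documents. Whole-number cases, with g = 0.5 assumed:

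- One user in 55: 1/55 × 0.5 = 0.9%.
- Three users in 55: 3/55 × 0.5 = 2.7%.
- One user among the 15 diabetic subjects: 1/15 × 0.5 = 3.3% of that group's change.

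**Step 3: effect on power.** Assume a two-sided paired t-test at 0.05 and an effect that gives 80% power when f = 0 (standardized paired effect 0.385 at n = 55, 0.454 at n = 40, 0.778 at n = 15). The sample size needed is multiplied by 1/(1 − f × g)².

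| f (assumed) | g (assumed) | Loss f × g | Power | N multiplier |
|---|---|---|---|---|
| 0 | any | 0% | 80% | 1.00 |
| 2% | 0.5 | 1% | 79% | 1.02 |
| 10% | 0.5 | 5% | 76% | 1.11 |
| 10% | 1.0 | 10% | 71% | 1.23 |
| 20% | 0.5 | 10% | 71% | 1.23 |
| 20% | 1.0 | 20% | 61% | 1.56 |

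The power column is nearly the same at n = 15, 40 and 55, because each is anchored at 80%. It holds the standard deviation fixed. Allowing for the mix of users and non-users lowers it a little further (at n = 15, the last row becomes 57%).

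**Step 4: how large can g be?** The study dose as written is 500 mg × 2 × 2 = 2000 mg/day. The quoted supplement ceiling is 1000 mg/day, or 1000/2000 = one half. If response were proportional to dose (an assumption), a user at that ceiling who stopped the supplement on joining would move from 1000 to 2000 mg/day and show half the full change, so g = 0.5. One who continued it would move from 1000 to 3000 mg/day, the same 2000 mg/day increment as a non-user, with no loss. A g near 1 requires the response to be saturated at or below half the study dose, which no section states.

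**Step 5: use begun after day 0.** The baseline is then untreated and day 28 carries extra, unrecorded exposure. This does not dilute the change. It makes the change no longer attributable to the stated dose.

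**The case against.** The strongest reply is that this is a wording gap with no demonstrated effect. Widely used is a market remark in a safety paragraph, not a prevalence among eligible volunteers. Screening includes a full history, which could bring supplement use to light. Staff meet subjects before each study to discuss diet, and the consent form, which is not in the public text, may tell subjects to take only study capsules.

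Much of this stands as a limit on size and certainty. A reader might infer four stronger things that the documents do not support:

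- *That the effect is diluted.* This needs users to be enrolled and their use to affect the endpoints. Neither is established.
- *That the loss is at least 5%.* That figure comes from assuming f of 10% or more. Nothing in the documents sets such a floor, and one user in 55 with half the effect present gives 0.9%.
- *That a user's paired change would be near zero.* Common supplement doses are at most half the written study dose, so carry-over may be partial.
- *That advertising will draw in users.* The protocol describes local advertising but does not say that the advertisements name resveratrol.

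The omission itself is not answered. A history may reveal use, but no rule tells the site what to do with the answer or to record it. A consent-form instruction would not replace an eligibility criterion.

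The Overview and Statistical Analysis also mention placebo, and the latter mentions randomization and 45 days. That conflicts with the open-label 28-day design described under General Experimental Conditions and Aim 1. If a placebo arm did exist, unrestricted outside use would still narrow the contrast.

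**Conclusion.** The point holds as a gap in eligibility and conduct that could bias the paired change toward no effect in all four aims. It does not show that bias will occur.

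The omission is certain on the text of the protocol; the size is not. It runs from about 0% if few or no users enrol to 20% of the true change if f = 20% and g = 1.0. Both of those values are assumptions, and the upper one requires full carry-over from doses at most half the study dose. Outside use begun after day 0 is a separate problem of misstated exposure, not dilution.

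The change should be made despite the uncertain size: day 0 is the only untreated reference, there is no stated power margin to absorb a loss, the diabetic group has only 15 subjects, and unrecorded use cannot be corrected afterwards.

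**What to change.** 1. Add to the exclusions in Study Population and Recruitment and in Human Subject Characteristics: current or recent use of a resveratrol-containing supplement, with a minimum interval before day 0 that the sponsor sets and justifies.
2. Instruct subjects to take no resveratrol supplement other than the study capsules through the second clamp.
3. Ask about such use at screening, day 0 and day 28, and record the answers, so that exposure is documented and a sensitivity analysis is possible.

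The instruction alone would not be enough. Step 4 of the working shows that a current user who is admitted and then told to stop is a case in which the paired change shrinks, so the exclusion is needed as well.

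The change is confined to supplements. The protocol also lists food sources but gives no amounts for them, so their contribution cannot be sized from the documents.

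Cost: one eligibility line, one instruction and one question at visits already planned. A few volunteers who take the supplement would be turned away. Study dose, schedule and procedures are unchanged.
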